4.2.1 Available data

Blood samples will be collected for the determination of efgartigimod concentration at the time points indicated in the schedule of assessments (see section 9.4).

Time windows for PK samples are specified as follows:

• Dosing days: within 2 hours prior to the start of infusion for the pre-dose PK sample; within 30 minutes after end of infusion for the post-dose PK sample.

All concentration data-points with deviations outside these permitted ranges will be excluded from the descriptive statistics on concentrations by scheduled timepoint, and a remark will be added in the appropriate listing.

The PK samples taken after a missed dose up to the next administered dose will be excluded from descriptive statistics and excluded from PK parameter derivation, a remark will be added in the appropriate listing.

4.2.2 Derivation rules

The following parameters from the individual serum drug concentration versus time profile for efgartigimod:

- C_{max}: maximum observed serum concentration
- C_{trough}: Serum concentration observed pre-dose

Concentration data-points with deviations outside the permitted time window (see section 4.2.1) will be excluded for the PK parameter derivation. C_{trough} will not be calculated at baseline and if the post-dose sample is missing, C_{max} will not be estimated.

4.2.3 **Presentation of results**

For tables by dosing frequency, only visits of the fixed dosing schedule period (i.e. baseline up to week 3 and week 16 up to week 24) will be tabulated. In this first period of baseline up to week 3, all patients have weekly dosing per protocol. For the second period, the dosing frequency is defined as explained in section 3.6.2.

SGS	Statistical Analysis Plan	
ARGX-113-1801	Final analysis	Final 1.0 of 28MAR2022

Individual concentration data and actual blood sampling times from start of IV infusion for PK assessments will be listed. Data issues like time deviations will be mentioned in the remarks.

Descriptive statistics on concentration data will be presented in tables per visit (and dosing frequency (weekly or q2w)) and per time point. A similar table will be created by ADA and by NAb Patient Classification.

Individual PK parameters will be listed.

Descriptive statistics on PK parameters will be presented in tables per visit (and dosing frequency (weekly of q2w)).

4.3 **PHARMACODYNAMICS**

4.3.1 Available data

The following PD parameters will be measured:

- total immunoglobulin G (IgG), IgG subtypes (IgG1, IgG2, IgG3, and IgG4)
- antiplatelet antibody levels targeting GPIIb/IIIa, GPIb/IX, GPV and GPIa/IIa.

For total IgG, it was decided to reanalyze the samples using an alternative assay. For the statistical analysis, only the results obtained with the immunoturbidimetry in vitro diagnostic (IVD) assay will be used and not the ELISA results.

4.3.2 Derivation rules

BLQ or ALQ values will not be imputed but excluded from the analysis.

Antiplatelet antibody positivity at a certain time point is defined as having at least one out of four values of the individually tested glycoproteins above the pre-defined optical density (OD) cutoff (0.128) at that time point.

Antiplatelet antibody positivity for a particular glycoprotein at a certain time point is defined as having an OD value above the pre-defined OD cutoff (0.128) for that particular glycoprotein at that time point.

4.3.3 Presentation of results

IgG subtypes will be listed only.

For tables by dosing frequency, only visits of the fixed dosing schedule period (i.e. baseline up to week 3 and week 16 up to week 24) will be tabulated. In this first period of baseline up to week 3, all patients have weekly dosing per protocol. For the second period, the dosing frequency is defined as explained in section 3.6.2.

For total IgG, summary statistics will be provided in terms of actual values and changes from baseline for each visit per dosing frequency and overall. Moreover, percent changes from baseline will also be presented. The summary statistics for total IgG will be repeated for all subgroups specified in section 4.1.4.

Frequency of antiplatelet antibody positive patients will be summarized per analysis visit and for the worst-case analysis visit. For antiplatelet antibodies against each glycoprotein (GPIIb/IIIa, GPIb/IX, GPV, GPIa/IIa) separately, frequency of patients

SGS	Statistical Analysis Plan	
ARGX-113-1801	Final analysis	Final 1.0 of 28MAR2022

positive for antiplatelet antibodies against the particular glycoprotein will be summarized per analysis visit and for the worst-case analysis visit.

All actual and change from baseline IgG and antiplatelet antibody levels data will be listed. Note that IgG results obtained with an ELISA assay will not be shown in the listings.

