#### Pharmacodynamics, Pharmacokinetics, and Immunogenicity

Descriptive statistics will be provided for PD parameters (total IgG and subtypes, and antiplatelet antibodies), and ADA. Efgartigimod serum concentration data will be summarized.

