### Other Secondary Endpoints Not Subject to Alpha Control:

- Percentage of patients with overall platelet response defined as achieving a platelet count of  $\geq 50 \times 10^9$ /L on at least 4 occasions at any time during the 24-week treatment period.
- Extent of disease control defined as the number of cumulative weeks until week 12, with platelet counts of  $\geq 50 \times 10^9$ /L.
- Percentage of patients with overall platelet response defined as achieving a platelet count of  $\geq 50 \times 10^9$ /L on at least 4 occasions at any time until week 12.
- Mean change from baseline in platelet count at each visit.
- Time to response defined as the time to achieve 2 consecutive platelet counts of  $\geq 50 \times 10^9 / L$ .
- Rate of receipt of rescue therapy (rescue per patient per month).

argenx BVBA Confidential Page 41 of 162

- Proportion of patients for whom dose and/or frequency of concurrent ITP therapies have increased at week 12 or later.
- The number of cumulative weeks over the planned 24-week treatment period with platelet counts  $\ge 30 \times 10^9$ /L and at least  $20 \times 10^9$ /L above baseline.
- In patients with baseline platelet count of  $<15\times10^9/L$ , the number of cumulative weeks over the planned 24-week treatment period with platelet counts of  $\ge 30\times10^9/L$  and at least  $20\times10^9/L$  above baseline.
- Change from baseline in PRO (FACIT-Fatigue, Fact-Th6) and QoL (SF-36) at planned visits.
- Incidence of anti-drug antibodies (ADA) to efgartigimod.
- Pharmacokinetic parameters of efgartigimod: maximum observed serum concentration (Cmax) and serum concentration observed predose (Ctrough).
- Pharmacodynamics markers: Total IgG, IgG isotypes (IgG1, IgG2, IgG3, IgG4), antiplatelet antibody levels.

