## 8.4.4. Pharmacodynamics, Pharmacokinetics, and Immunogenicity

[figure not shown]
Descriptive statistics will be provided for PD parameters (total IgG and subtypes, and antiplatelet antibodies) and ADA. Efgartigimod serum concentration data will be summarized.

argenx BVBA Confidential Page 85 of 162

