- 14) Proportion of patients achieving platelet counts of at least $\geq 50 \times 10^9$ /L for at least 8 out of 12 visits between weeks 13 and 24 of the study.
- 15) Proportion of patients with an IWG-Complete response¹².
- 16) Proportion of patients with an IWG-Response¹¹.
- 17) Proportion of patients with an IWG-Initial Response¹³.

The definition of the PK analysis set as specified in this SAP deviates from the definition of the CTP. The definition was updated to specify that placebo subjects are excluded from the PK analysis set.

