14.2.8.1.2	Descriptive Statistics of Efgartigimod Serum Concentrations (unit) by Visit (and Dosing Frequency) and Time Point by ADA Patient Classification	РК	
14.2.8.1.3	Descriptive Statistics of Efgartigimod Serum Concentrations (unit) by Visit (and Dosing Frequency) and Time Point by NAb Patient Classification	РК	

SGS	Statistical Analysis Plan	
ARGX-113-1801	Final analysis	Final 1.0 of 28MAR2022

14.2.8.2	Descriptive Statistics of Efgartigimod PK Parameters by Visit (and Dosing Frequency)	РК
PHARMACOD	DYNAMICS	
14.2.9.1	Descriptive Statistics of Actual Values and Changes from Baseline in Total IgG Level by Dosing Frequency and Overall and by Visit	
14.2.9.2.1	Descriptive Statistics of Actual Values and Changes from Baseline in Total IgG by Dosing Frequency and Overall and by Visit by History of Splenectomy	PD
14.2.9.2.2	Descriptive Statistics of Actual Values and Changes from Baseline in Total IgG by Dosing Frequency and Overall and by Visit by Receiving Concurrent ITP Therapies at Baseline	PD
14.2.9.2.3	Descriptive Statistics of Actual Values and Changes from Baseline in Total IgG by Dosing Frequency and Overall and by Visit by Baseline Platelet Count	PD
14.2.9.2.4	Descriptive Statistics of Actual Values and Changes from Baseline in Total IgG by Dosing Frequency and Overall and by Visit by Number of Prior ITP Therapies	PD
14.2.9.2.5	Descriptive Statistics of Actual Values and Changes from Baseline in Total IgG by Dosing Frequency and Overall and by Visit by Time Since Diagnosis	PD
14.2.9.2.6	Descriptive Statistics of Actual Values and Changes from Baseline in Total IgG by Dosing Frequency and Overall and by Visit by Sex at Birth	PD
14.2.9.2.7	Descriptive Statistics of Actual Values and Changes from Baseline in Total IgG by Dosing Frequency and Overall and by Visit by Region	PD
14.2.9.2.8	Descriptive Statistics of Actual Values and Changes from Baseline in Total IgG by Dosing Frequency and Overall and by Visit by Age Category	PD
14.2.9.2.9	Descriptive Statistics of Actual Values and Changes from Baseline in Total IgG by Dosing Frequency and Overall and by Visit by Race	PD
14.2.9.2.10	Descriptive Statistics of Actual Values and Changes from Baseline in Total IgG by Dosing Frequency and Overall and by Visit by Ethnicity Category	PD
14.2.9.2.11	Descriptive Statistics of Actual Values and Changes from Baseline in Total IgG by Dosing Frequency and Overall and by Visit by Weight Category at Baseline	PD

SGS	Statistical Analysis Plan	

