16.2.3.1	Patients Excluded from the Efficacy Analysis		FAS	
16.2.4.1	Demographic Data		SAF	
16.2.4.2	Baseline Disease Characteristics		SAF	
16.2.4.3	Medical History		SAF	
16.2.4.4	ITP History		SAF	
16.2.4.5	Prior Vaccinations		SAF	
16.2.4.6	Prior and Concomitant Therapies		SAF	
16.2.4.7	Prior ITP Therapies		SAF	
16.2.4.8	Concurrent ITP Treatment		SAF	
16.2.4.9	Rescue ITP Treatment		SAF	
16.2.5.1	Administration of Study Drug		SAF	

	SGS Statistical Analysis Plan	
ARC	X-113-1801 Final analysis	Final 1.0 of 28MAR2022

PHARMACOKINETICS

16.2.5.2	Individual Efgartigimod Serum Concentrations and Actual Blood Sampling Times	РК
16.2.5.3	Individual Efgartigimod PK Parameters	РК
EFFICACY		
16.2.6.1.1	Different Response Definition Outcomes Part 1	FAS
16.2.6.1.2	Different Response Definition Outcomes Part 2	FAS
16.2.6.1.3	Different Response Definition Outcomes Part 3	FAS
16.2.6.2	Platelet Count Results	FAS
16.2.6.3	Bleeding Events	FAS
16.2.6.4	PRO: FACT-Th6 and FACIT	FAS
16.2.6.5	QoL: SF-36	FAS
PHARMAC	DDYNAMICS	
16.2.6.6	Total IgG, IgG Subtypes and Antiplatelet Antibodies: Actual Values and Percent Changes From Baseline	PD
ANTI-DRUG	ANTIBODIES	
16.2.6.7	Anti-drug Antibodies and Neutralizing Antibodies to Efgartigimod	SAF
SAFETY		
ADVERSE E	VENTS	
16.2.7.1	Adverse Events	SAF
16.2.7.2	Serious Adverse Events	SAF
16.2.7.3	Fatal Adverse Events	SAF
16.2.7.4	Treatment-Emergent Adverse Events for Which the Study or the Study Drug Were Discontinued or Interrupted	SAF
16.2.7.5	Adverse Events of Special Interest	SAF
16.2.7.6	Infusion Related Reactions	SAF
16.2.7.7	Adverse Events: Coding Information	SAF
16.2.7.8	Listing of Abnormal Physical Examination Results	SAF
LABORATO	RY DATA	
16.2.8.1	Laboratory Test Results for Patients with Abnormal Values	SAF
VITAL SIGN	NS	
16.2.9.1	Vital Signs Results for Patients with Abnormal Values	SAF
ECG		
16.2.10.1	ECG Results for Patients with Abnormal Values	SAF

SGS	SGS Statistical Analysis Plan	
ARGX-113-1801	Final analysis	Final 1.0 of 28MAR2022

9. **APPENDICES**

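### IgG1 to IgG4 are secondary PD markers with promised descriptive statistics, but the SAP only lists them per patient and does not record this as a departure from the protocol

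*SAP*

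**What the plan says.** Protocol section 3.2 includes this among the secondary endpoints outside alpha control: "Pharmacodynamics markers: Total IgG, IgG isotypes (IgG1, IgG2, IgG3, IgG4), antiplatelet antibody levels". SAP 1.2.2 carries the same endpoint. On analysis, protocol 8.4.4 commits to the following: "Descriptive statistics will be provided for PD parameters (total IgG and subtypes, and antiplatelet antibodies) and ADA". The synopsis makes the same commitment.

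SAP 4.3.3 opens with "IgG subtypes will be listed only". For the total it is much fuller: "For total IgG, summary statistics will be provided in terms of actual values and changes from baseline for each visit per dosing frequency and overall". Percent changes from baseline and repeats by subgroup are added for total IgG.

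The only planned output that carries the subtypes is listing 16.2.6.6, titled "Total IgG, IgG Subtypes and Antiplatelet Antibodies: Actual Values and Percent Changes From Baseline".

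SAP 6.1, the section for changes not covered by protocol amendments, describes the Cochran-Mantel-Haenszel analysis of the primary endpoint and 17 extra analyses. It ends with the PK set: "The definition of the PK analysis set as specified in this SAP deviates from the definition of the CTP". It has no entry on IgG subtypes, and sections 6.2 and 6.3 are marked not applicable.

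**The concern.** A protocol that names four markers and promises descriptive statistics for them sets an expectation of group-level results. A patient listing does not meet it. The clinical trial report would contain no mean, median, change or percent change for any subtype, by arm or by visit, unless someone produced one outside the plan.

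This matters in a modest way. Protocol 1.2 cites a phase 2 reduction in all IgG subtypes as part of the case for the drug. As the SAP stands, the phase 3 trial produces no planned summary to set beside that statement, although the samples are scheduled before dosing at infusion visits (protocol 7.5 and the schedule of assessments).

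The second issue is documentation. Someone who reads only SAP section 6 to learn where the analysis departs from the protocol would not find this change or a reason for it.

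**Working it through.** No power, alpha or effect-size figure bears on this point, so the check compares the texts and counts the planned outputs.

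1. **Was a summary promised?** Yes. Protocol 8.4.4 and the synopsis ("Descriptive statistics will be provided for PD parameters (total IgG and subtypes, and antiplatelet antibodies), and ADA") both name the subtypes explicitly. SAP 2.4.1 defines what descriptive statistics contain: number of observations, mean, SD, median, quartiles and range, with the standard error added for PD. A listing of individual values is not that.

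2. **Is a summary planned?** The PD tables in the SAP 8.1 index are:
   - 14.2.9.1, total IgG, whose title includes "Baseline in Total IgG Level by Dosing Frequency and Overall and by Visit": 1 table
   - 14.2.9.2.1 to 14.2.9.2.13, total IgG by 11 baseline subgroups plus ADA and NAb classification: 13 tables
   - 14.2.9.3, antiplatelet antibody categories: 1 table

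   Total: 1 + 13 + 1 = 15 tables. Fourteen concern total IgG, one concerns antiplatelet antibodies, and 0 concern IgG1, IgG2, IgG3 or IgG4.

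3. **How many patients are involved?** Planned enrolment is about 117 chronic plus up to 39 persistent patients, so at most about 117 + 39 = 156. The PD analysis set may be smaller, because SAP 2.1.1 requires treatment and at least one post-dose PD measurement.

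4. **Is the change disclosed?** In part. The introduction to protocol section 8 asks that changes to the analysis methods be mentioned in the SAP. The sentence in SAP 4.3.3 mentions the handling. It does not say that it differs from protocol 8.4.4, and it gives no reason. Section 6.1 omits it, while recording the exclusion of placebo patients from the PK set.

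5. **Could the summary be produced?** Mostly, on the text. SAP 2.2.2 sets a baseline rule for total IgG and subtypes that accepts only IVD results, which implies that IVD subtype results exist. SAP 4.3.2 says how values outside the quantification limits are treated. However, SAP 4.3.1 describes re-analysis with an alternative assay for total IgG only, and SAP 4.3.3 keeps ELISA IgG results out of the listings. Nothing states which assay gave the subtype values. If it was ELISA alone (an assumption), these rules would leave nothing to tabulate and perhaps nothing to list.

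**The case against.** The strongest reply is that little is lost and nothing is hidden. Much of that stands.

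- A reader might infer that the trial cannot meet its PD objective. The documents do not support this. The objective is to assess PD effects in general, with no separate objective for subtypes, and the total IgG and antiplatelet antibody tables address it.
- A reader might infer that a treatment-effect estimate has been dropped. None was promised. The protocol commits to description only, with no model, comparison or alpha. Listing 16.2.6.6 would also let group summaries be derived later, if it is populated.
- A reader might infer that the change was concealed or made after the fact. It was not. It is written plainly in the approved SAP, Final 1.0 of 28 March 2022. What is missing is its identification as a departure and a reason.
- A reader might infer that a summary certainly needs no new data. That depends on usable IVD subtype results, which the documents imply but do not confirm.

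None of this removes the mismatch. The protocol promises a summary by name, the SAP withdraws it, and no sponsor redaction or extraction gap accounts for the difference.

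**Conclusion.** The point holds as a minor inconsistency between protocol and SAP. Four named secondary markers have a promised descriptive summary that the SAP replaces with a patient listing, and the replacement is neither identified as a departure nor justified in SAP 6.1. The loss is the group description of IgG1 to IgG4 by arm and visit. The primary and key secondary analyses are untouched, and no alpha-controlled conclusion changes.

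This rests on the table and listing indexes in SAP 8.1 and 8.2 being complete. Whether the summary can be produced from existing results rests on one unconfirmed assumption, that subtype values from an IVD assay are available.

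**What to change.** Repeat table 14.2.9.1 for IgG1, IgG2, IgG3 and IgG4, showing actual value, change and percent change from baseline by visit and arm. Use the IVD results that SAP 2.2.2 says will be considered, and amend the opening sentence of SAP 4.3.3 to match. The subgroup repeats planned for total IgG are not needed. State in SAP 4.3.1 which assay produced the subtype values.

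The cost is four more parameters to tabulate in a layout already planned for total IgG. If IVD subtype results exist, no new data are needed.

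If no usable IVD subtype results exist, keep the listing-only handling and record it in SAP 6.1 as a departure from protocol 8.4.4, with the reason. In that case also check that listing 16.2.6.6 can be populated under the rule that excludes ELISA results.

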# 2.2. Secondary Objectives

- To evaluate the efficacy of efgartigimod compared to placebo in overall platelet count response.
- To evaluate the safety and tolerability of efgartigimod administered IV weekly or q2w.
- To evaluate the incidence and severity of bleeding events while receiving treatment with efgartigimod compared to placebo.
- To evaluate the use of rescue treatment and changes in concurrent ITP therapy while receiving treatment with efgartigimod compared to placebo.
- To evaluate the effects of efgartigimod treatment on QoL measures and PRO compared to placebo.
- To assess the immunogenicity of efgartigimod.
- To assess the PK of efgartigimod.
- To assess the PD effects of efgartigimod.

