### 4.3.2. Exclusion Criteria

Patients will not be enrolled in this trial if they meet any of the following criteria:

argenx BVBA Confidential Page 49 of 162

- 1. ITP/thrombocytopenia associated with another condition, eg, lymphoma, chronic lymphocytic leukemia, viral infection, hepatitis, induced or alloimmune thrombocytopenia, or thrombocytopenia associated with myeloid dysplasia.
- 2. Use of anticoagulants (eg, vitamin K antagonists, direct oral anticoagulants) within 4 weeks prior to randomization.
- 3. Use of any transfusions within 4 weeks prior to randomization.
- 4. Use of Ig (IV, SC, or intramuscular route) or plasmapheresis (PLEX), 4 weeks prior to randomization.
- 5. Use of anti-CD20 therapy (eg, rituximab) within 6 months prior to randomization.
- 6. Use of romiplostim within 4 weeks prior to randomization.
- 7. Undergone splenectomy less than 4 weeks prior to randomization.
- 8. Use of any other investigational drug within 3 months or 5 half-lives of the drug (whichever is longer) prior to randomization.
- 9. Use of monoclonal antibodies or Fc fusion proteins, other than those previously indicated, within 3 months prior to randomization.
- 10. At the screening visit, clinically significant laboratory abnormalities as below:
  - Hemoglobin ≤9 g/dL
    - OR -
  - International normalized ratio >1.5 or activated partial thromboplastin time >1.5×ULN
    - OR -
  - Total IgG level <6 g/L
- 11. Patients who have a history of malignancy, including malignant thymoma, or myeloproliferative or lymphoproliferative disorders, unless deemed cured by adequate treatment with no evidence of recurrence for ≥3 years before screening. Patients with completely excised non-melanoma skin cancer (such as basal cell carcinoma or squamous cell carcinoma) or cervical carcinoma in situ would be permitted at any time.
- 12. Uncontrolled hypertension, defined as a repeated elevated blood pressure exceeding 160 mmHg (systolic) and/or 100 mmHg (diastolic) despite appropriate treatments.
- 13. History of any major thrombotic or embolic event (eg, myocardial infarction, stroke, pulmonary embolism, deep venous thrombosis) within 12 months prior to randomization.
- 14. History of coagulopathy or hereditary thrombocytopenia or a family history of thrombocytopenia.
- 15. History of a recent or planned major surgery (that involves major organs eg, brain, heart, lung, liver, bladder, or gastrointestinal tract) within 4 weeks of randomization.

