### **6.8.4.** Rescue Therapy

"Rescue therapy" is defined as an occurrence where the patient needs treatment with 1 or more rescue treatments. An "occurrence" is defined as a period of maximum 5 days where 1 or more rescue treatments are administered simultaneously or consecutively to the trial patient. The start date/time of the occurrence is the start of the administration of the first rescue treatment.

Rescue therapy is allowed for patients having protocol-defined ITP clinical deterioration AND if in addition the treating physician believes that the patient's health is in jeopardy if rescue therapy is not given.

Rescue therapy is allowed post-baseline during the 24-week trial period for patients with a platelet count of  $<30\times10^9$ /L and 1 of the following:

- an immediate risk of bleeding or a clinically significant bleeding, or wet purpura
- requirement for urgent or emergent surgery (elective surgeries must be postponed until trial completion)

The following rescue therapies are permitted:

- IV methylprednisolone up to 1 g/day  $\times$  1-3 days, oral dexamethasone up to 40 mg/day  $\times$  1-3 days, or oral prednisone up to 1 mg/kg/day  $\times$  1-2 days
- IVIg: up to 1 g/kg/day  $\times$  1-2 days
- IV anti-D: up to 50-75 mcg/kg/day × 1-2 days Note: Anti-D rescue therapy should not be given to Rh(D)-positive patients
- platelet transfusions

If a patient needs rescue therapy according to the investigator, it is encouraged to inform the medical monitor at the sponsor's designated CRO, whenever possible prior to actual implementation of the rescue therapy.

In the event of rescue with IVIg or IV anti-D:

argenx BVBA Confidential Page **63** of **162** 

If given at a visit where the IMP was due to be administered, the IMP should be withheld and administered at the next visit (see also Section 4.5 and Section 6.11).

For rescue therapy with methylprednisolone, dexamethasone, prednisone, or platelet transfusions:

Administration of the IMP continues during rescue therapy

Patients who were receiving q2w dosing at the time of rescue therapy will have the IMP administration frequency increased to weekly.

For patients who receive rescue therapy, the platelet counts for 4 weeks after the first day of the rescue treatment will not be used (ie, are censored) to assess whether or not the patient can transition to q2w treatment.

Patients requiring more than 3 occurrences of rescue therapy will discontinue from IMP.

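### Total IgG is summarised with no rule for samples taken after IVIg rescue, so infused IgG is counted in the pharmacodynamic result

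*SAP*

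**What the plan says.** Protocol 2.2 lists a secondary objective, "To assess the PD effects of efgartigimod", and Protocol 3.2 gives the matching endpoints outside alpha control: "Pharmacodynamics markers: Total IgG, IgG isotypes (IgG1, IgG2, IgG3, IgG4), antiplatelet antibody levels". SAP 4.3.3 sets out the analysis: "For total IgG, summary statistics will be provided in terms of actual values", and also as changes from baseline, by visit, both split by dosing frequency and for all patients together. Percent changes are added, and the summaries are repeated for every subgroup in SAP 4.1.4. SAP 4.4.3 adds percent change in total IgG by ADA and NAb category, for efgartigimod-treated patients. For the subtypes, SAP 4.3.3 says "IgG subtypes will be listed only".

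Protocol 6.8.4 permits immunoglobulin as rescue, "IVIg: up to 1 g/kg/day", for one or two days. If it falls on a dosing visit, that dose is skipped and given at the next visit. A q2w patient who is rescued moves to weekly dosing. IMP stops only after more than three rescue occurrences.

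Elsewhere the documents do guard against this kind of interference:
- Protocol 4.3.2 excludes patients for "Use of Ig (IV, SC, or intramuscular route) or plasmapheresis (PLEX), 4 weeks prior to randomization".
- SAP 4.1.2.2 treats platelet counts in the 4 weeks after the start of rescue as below the response threshold.
- SAP 4.2.1 has a sample-level rule for drug concentrations: "The PK samples taken after a missed dose up to the next administered dose will be excluded from descriptive statistics".

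**The concern.** The objective is to describe what efgartigimod does to IgG. SAP 4.3.1 uses an immunoturbidimetric assay, and nothing in the documents describes a way to tell infused IgG from the patient's own. A sample drawn while infused IgG is still circulating mixes the drug's effect with the rescue treatment. On efgartigimod this makes the reduction look smaller. On placebo it can look like a rise.

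The same values feed the by-visit, subgroup and ADA/NAb tables, and in a small category one or two such samples can move a mean noticeably. The dosing-frequency table deserves a mention. Moving to q2w requires counts of at least 100×10⁹/L, rescue requires a count below 30×10⁹/L, and rescue returns a q2w patient to weekly dosing. Affected samples would therefore tend to fall in the weekly column.

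**Working it through.** **1. Is there any rule that removes these samples?** The plan states no figure for total IgG that could be reproduced, so the check is a trace of every rule that could apply.
- PD analysis set (SAP 2.1.1): treated patients with at least one post-dose PD value. No condition on rescue.
- Analysis windows (SAP 2.2.4): all assessments are allocated, unscheduled ones included. No condition on rescue.
- Outliers (SAP 2.3.4): none are removed; all measured values are used.
- Assay (SAP 4.3.1): ELISA results are dropped.
- Derivation (SAP 4.3.2): values below or above the quantification limits are dropped.
- Handling after intercurrent events (SAP 4.1.3.6): replacement by baseline applies to platelet counts, PRO and QoL, not to IgG.

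No rule reaches a total IgG value measured after IVIg.

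**2. Would such samples be collected?** Yes, if IVIg rescue occurs. Protocol 7.5 samples predose at IMP visits. The schedule of assessments adds the End-of-Treatment/Early Discontinuation visit, both follow-up visits and unscheduled visits. When IVIg is given on a dosing visit, the next routine sample comes one visit later and also follows a skipped dose.

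**3. How far does an arm mean move?** Let f be the share of an arm's samples at a visit that are affected, and d the rise per affected sample in percentage points of baseline. Then shift = f × d. Both are assumptions; the documents give neither.

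To place d: with an assumed baseline of 10 g/L and the 65% maximum mean reduction quoted from phase 2 in Protocol 1.2, a patient sits at 3.5 g/L. An assumed residual of 5 g/L gives 8.5 g/L. The change reads (8.5 − 10)/10 = −15% instead of −65%, so d = 50.

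Shift in points (efgartigimod mean if the clean value is −65%):

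| d | f = 2% | f = 5% | f = 10% | f = 20% |
|---|---|---|---|---|
| 25 | 0.5 (−64.5) | 1.25 (−63.75) | 2.5 (−62.5) | 5 (−60) |
| 50 | 1 (−64) | 2.5 (−62.5) | 5 (−60) | 10 (−55) |
| 100 | 2 (−63) | 5 (−60) | 10 (−55) | 20 (−45) |

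**4. What happens between arms?** The difference shifts by (f on efgartigimod − f on placebo) × d. Take a clean difference of −65 (placebo assumed at 0%) and d = 50:
- 5% on efgartigimod, 20% on placebo: −65 + (0.05 − 0.20) × 50 = −72.5, so the difference is inflated.
- 10% on efgartigimod, 5% on placebo: −65 + (0.10 − 0.05) × 50 = −62.5, so it is shrunk.

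**5. What rescue rate do these shares imply?** Assume weekly sampling, a 4-week effect and no overlap between courses. A share f at every one of 24 weeks then needs f × 24/4 courses per patient. With up to 156 patients at 2:1, there are up to 104 on efgartigimod.
- f = 2%: 0.12 courses per patient, about 12 courses.
- f = 10%: 0.6 per patient, about 62 courses.
- f = 20%: 1.2 per patient, about 125 courses.

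The larger shares therefore need heavy IVIg use if they are to hold across the whole period, though a single visit or a small subgroup could reach them.

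**The case against.** The strongest reply is that this is a descriptive secondary output, that an as-observed summary is a legitimate choice, and that the SAP makes that choice for bleeding. IgG values and rescue treatments are both listed, so a reader could find the affected samples. Medians and quartiles are planned and are less sensitive than means. Extreme values may drop out as above the assay limit. IVIg is only one of several rescue options. Protocol 1.1 says that FcRn blockade speeds the degradation of all IgG, so infused IgG should clear faster on efgartigimod than a fixed residual implies. Finally, excluding samples because of a post-randomisation event removes values selectively from poorly controlled patients.

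Most of this stands, and it limits the size and severity. It does not close the gap. For bleeding the SAP names its strategy; SAP 4.3 names none for IgG. The listings only allow an unplanned repair afterwards. The selection argument is a reason to keep both tables.

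A reader might infer more than the documents support:
- That total IgG is the main PD endpoint. It is one of three marker groups, though the only IgG marker tabulated.
- That contamination is certain, or that the first sample always comes about 7 days after IVIg. It depends on IVIg being used, and that interval applies only to IVIg given on a dosing visit. Sampling is not confined to IMP visits.
- That IgG tables by responder status are distorted most. SAP 4.1.4 lists no responder subgroup; dosing frequency is the nearest, and its table covers only baseline to week 3 and weeks 16 to 24.
- That the drug–placebo contrast must be understated. Step 4 shows it can go either way.

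**Conclusion.** The gap is real. Followed as written, the plan counts infused IgG in the total IgG summaries. Within an arm the push is upward, so the reduction on efgartigimod is understated wherever IVIg rescue occurs there; the between-arm direction is open. The size is unknown. With an assumed 50-point rise per affected sample, it is about 1 point at 2% affected and 5 points at 10%. That rests on assumed values for baseline, residual IgG and share affected, and makes no allowance for faster clearance on efgartigimod. The primary and key secondary tests use platelet counts and bleeding assessments and are not affected. This is an inexpensive improvement to a secondary analysis and does not threaten the trial's main conclusions.

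**What to change.** Add a rule to SAP 4.3.2: total IgG results obtained within a stated window after the start of any IVIg administration are excluded from the by-visit, dosing-frequency, subgroup and ADA/NAb summaries. Four weeks is a reasonable choice if stated as a convention. It matches the Ig washout before randomisation and the platelet rule after rescue, but no IgG kinetics in the documents support it. Flag the affected total IgG and subtype values in the listing; the subtypes need nothing more, as they are not summarised. Report the number of values excluded per arm and visit. Keep the all-values summary as a supportive table.

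The cost is one derivation rule, one flag and a repeated table. IVIg rescue is already coded in SAP 3.5.2, and other IVIg use can be found from the same drug coding. The downside is slightly fewer IgG values at some visits, and an exclusion that depends on a post-randomisation event, which is why the as-observed table stays. No dosing or rescue rule changes.
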